11.2.1.1.2 Photographs for Independent, Blinded Evaluation

To assess the proportion of treated subjects with eyebrow lift from baseline to Day 90 (i.e., primary effectiveness endpoint) and to Day 180 (i.e., secondary effectiveness endpoint), three independent, blinded evaluators will assess paired, 2D photograph sets of treated subjects and untreated individuals, according to the procedure described below. These evaluators will be experienced, non-treating physicians, who are board-certified in an appropriate specialty (e.g., dermatology, plastic surgery, etc.).

One image set, containing frontal and oblique views, will be paired as follows:

- Set 1 (treated subjects only): Photograph 1 (baseline) vs. Photograph 2 (Day 90 or Day 180 post-treatment);
- Set 2 (untreated individuals only): Photograph 1 (“baseline”) vs. Photograph 2 (post-baseline).

Image sets will be randomly distributed for presentation to the blinded evaluators. Photograph 1 will be identified, and the independent evaluators will be blinded to the random distribution of treated versus untreated status of the comparator Photograph 2 (i.e., Day 90 or Day 180 post-treatment among treated subjects or post-baseline for untreated individuals). The blinded evaluators will be informed that the photographs for review will include both treated subjects and untreated individuals. However, they will not be informed of the ratio of untreated to treated subjects, nor will they be informed of how many subjects are treated/untreated.

For each image set, blinded evaluators will assess each photograph and will be asked the following: “Using Photograph 1 as a reference, which of the following best characterizes the change in appearance of the eyebrow observed in the comparator Photograph 2: Eyebrow Lift or No Eyebrow Lift?”.

Lift will be declared if at least two blinded evaluators indicate “Eyebrow Lift” for the comparator photograph.

Additional information on the methodological plan, detailing photograph collection through subsequent presentation to blinded evaluators, will be provided in a supporting document, developed collaboratively between the sponsor and the photography vendor.

This assessment will be proctored by the central photography vendor.

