#### 6.1.1 Primary Effectiveness Endpoint

##### 6.1.1.1 Primary analysis

The primary endpoint of the study is the proportion of treated subjects with eyebrow lift by comparing photographs taken at Day 90 (post-treatment) with baseline (pre-treatment) photographs.

Each independent evaluator will assess “Eyebrow Lift”, “No Eyebrow Lift” or “Cannot Evaluate” between Photograph 1 (baseline) and Photograph 2 (post-baseline). Photograph 1 will be identified, and the independent evaluators will be blinded to the random distribution of treated versus untreated status of the comparator Photograph 2 (i.e., Day 90 post-treatment among treated subjects or post-baseline for untreated individuals). Lift will be declared if at least two blinded evaluators indicate “Eyebrow Lift” for the comparator photograph. In case at least two evaluators declare a photograph as not assessable (i.e., “Cannot Evaluate” is ticked), the corresponding lift score over all evaluators will be set to missing for the primary analysis. In case one evaluator rates a photograph as “Cannot Evaluate” and the other two evaluators disagree, the overall lift score will be set to “No Lift”.

The point estimate for the proportion of subjects fulfilling the primary endpoint will be described by frequency statistics for the ITT subset.

[figure not shown]
Effectiveness is established if:

[figure not shown]
- A. the point estimate is  $\geq 65\%$  and
- B. the lower bound of the one-sided 95% Wilson CI is  $> 50\%$ .

In addition, the proportion of untreated individuals fulfilling the primary endpoint will be calculated. It is expected that the point estimate for the proportion of untreated individuals is  $< 50\%$ .

Missing data, including a missing primary endpoint assessment in subjects with unacceptable (i.e. unassessable) or missing photographs at baseline or Day 90, will be imputed by multiple imputation. In case of complete data, no multiple imputation will be performed and the primary analysis is based on complete data for the ITT.

Imputation is done 50 times using a fully conditional specification logistic regression method, as implemented in SAS PROC MI with statement FCS LOGISTIC, and will use the investigational site and the baseline characteristics age and BMI as independent variables.

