### 6.1.1.2 Sensitivity analyses

To assess sensitivity of the results, the primary analyses will be repeated for:

- PP population with observed cases,
- ITT with observed cases, and
- ITT with missing value treated as no eyebrow lift (worst case analysis).

Observed cases are those not missing on primary analysis (section 6.1.1.1).

[figure not shown]
Additionally, further sensitivity analyses will be performed with regard to image quality as assessed by the central photography vendor. The following analyses will be performed, treating assessments that are based on photographs with not approved image quality as missing:

- PP population with observed cases,
- ITT with observed cases, and
- ITT with missing values imputed by multiple imputation.

For the sensitivity analysis using multiple imputation approach, similar methods as described in section 6.1.1.1 will be performed.

For all other sensitivity analyses, results can be taken directly from the SAS proc freq output:

CCI

, where response\_data is the dataset with overall lift data per subject. The point estimate for the proportion of responders and the lower limit of the one-sided 95% Wilson CI will be used to assess sensitivity.

A sensitivity analysis will not be done, if identical to any other analysis.

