### 6.1.2 Secondary Effectiveness Endpoints

#### Independent Photographic Review for Eyebrow Lift at Day 180

The secondary endpoint will only be assessed among Stage 1 subjects who reconsented for extended study participation and all Stage 2 subjects.

The secondary endpoint of the study is the proportion of treated subjects with eyebrow lift by comparing photographs taken at Day 180 (post-treatment) with baseline (pre-treatment) photographs.

Each independent evaluator will assess “Eyebrow Lift”, “No Eyebrow Lift” or “Cannot Evaluate” between Photograph 1 (baseline) and Photograph 2 (post-baseline). Photograph 1 will be identified, and the independent evaluators will be blinded to the random distribution of treated versus untreated status of the comparator Photograph 2 (i.e., Day 180 post-treatment among treated subjects or post-baseline for untreated individuals). Lift will be declared if at least two blinded evaluators indicate “Eyebrow Lift” for the comparator photograph. In case at least two evaluators declare a photograph as not assessable (i.e., “Cannot Evaluate” is ticked), the corresponding lift score over all evaluators will be set to missing for the secondary analysis.

The point estimate for the proportion of subjects fulfilling the qualitative eyebrow lift will be described by frequency statistics for the ITT subset, including the one-sided 95% Wilson CI.

Missing data, including a missing secondary endpoint assessment in subjects with unacceptable or missing photographs at baseline or Day 180, will be imputed by multiple imputation 50 times. Imputation is done using a fully conditional specification logistic regression method, as implemented in SAS PROC MI with statement FCS LOGISTIC, and will use the investigational site and the baseline characteristics age and BMI as informing variables. Point estimate and Wilson CI will be calculated with methods as described in Section 6.1.1.1. For implementation, SAS code similar to the statements for the primary endpoint will be used.

Sensitivity analyses and subgroup analyses will be performed similar to the primary endpoint.

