## **6.4 Special Statistical/Analytical Issues**

### **6.4.1 Discontinuations and Missing Data**

#### **Independent Photographic Review for Eyebrow Lift at Day 90 and Day 180**

For analysis of the primary and secondary effectiveness endpoints regarding Independent Photographic Review for Eyebrow lift, the following procedure for incomplete data from the independent evaluators will be applied:

[figure not shown]
- If data from all three independent evaluators is missing, the outcome of the subject will be set to missing.
- If the result of two out of three evaluators is missing, the outcome of the subject will be set to missing.

- If the result of one evaluator is missing and the other two evaluators agree on the assessment “Eyebrow Lift” then the outcome of the subject is set to “lift” for all analyses.
- If the result of one evaluator is missing and the other two evaluators agree on the assessment “No Eyebrow Lift” then the outcome of the subject is set to “no lift” for all analyses.
- If the result of one evaluator is missing and the other two evaluators disagree, then the outcome of the subject will be set to missing.

For treated subjects with missing outcome, the multiple imputation technique will be employed as described above for the primary and secondary analyses. For the worst case analysis, these subjects will be analyzed as having “no lift”.

All other effectiveness data will be analyzed as observed with no imputation of missing values. The denominator for percentages will be all subjects in the respective analysis set or population (i.e., missing data for binary or categorical variables will be presented as a separate possible category ‘Missing’).

CCI

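### Does the SAP score one 'Cannot Evaluate' rating with a 1-1 split in two conflicting ways?

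*SAP*

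**What the plan says.** SAP 6.1.1.1 gives each evaluator three possible ratings at Day 90: lift, no lift, or 'Cannot Evaluate'. Lift needs at least two lift ratings. Two or more 'Cannot Evaluate' ratings make the subject's overall score missing. If there is one 'Cannot Evaluate' "and the other two evaluators disagree, the overall lift score will be set to" 'No Lift'. The section then lists what is imputed, including "a missing primary endpoint assessment in subjects with unacceptable (i.e. unassessable) or missing photographs at baseline or Day 90".

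SAP 6.4.1, under a heading that covers Day 90 and Day 180, says that "the following procedure for incomplete data from the independent evaluators will be applied". Its last rule reads "If the result of one evaluator is missing and the other two evaluators disagree, then the outcome of the subject will be set to missing". Missing outcomes are multiply imputed in the primary analysis and counted as no lift in the worst-case analysis.

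Three other places bear on the point:

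- SAP 6.1.2 (Day 180) has the same three ratings and the same two-lift requirement. With two or more 'Cannot Evaluate', "the corresponding lift score over all evaluators will be set to missing for the secondary analysis". It does not repeat the sentence about a split.
- SAP 6.1.1.2 fixes the observed-case set: "Observed cases are those not missing on primary analysis (section 6.1.1.1").
- Protocol 11.2.1.1.2 asks evaluators for the "change in appearance of the eyebrow observed in the comparator Photograph 2: Eyebrow Lift or No Eyebrow Lift", with no third option.

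**The concern.** No sentence says whether 'Cannot Evaluate' counts as a missing result. If it does, 6.4.1 makes a one-lift, one-no-lift, one-'Cannot Evaluate' subject missing and imputes the outcome. If it does not, 6.1.1.1 makes that subject an observed failure.

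Some of the text seems to favour the first reading. Section 6.1.1.1 describes 'Cannot Evaluate' as not assessable and later lists unassessable photographs among the data to be imputed. Two 'Cannot Evaluate' ratings also have the same consequence as two missing results. At Day 180 the split sentence is absent, so the same ratings might be coded differently at the two visits.

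The primary conclusion would be at stake. Success requires a point estimate of at least 65%, and one or two subjects can decide that in a study of 40 to 50. If the reading were chosen once ratings were in hand, the choice could be steered by the result.

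**Working it through.** **1. Where the two readings differ.** L = lift, N = no lift, C = 'Cannot Evaluate'.

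| Ratings | SAP 6.1.1.1 | SAP 6.4.1, if C were treated as missing |
|---|---|---|
| L, L, C | lift | lift |
| N, N, C | lift not declared | no lift |
| L, N, C | 'No Lift' | missing, then imputed |
| two or three C | missing | missing |

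Only the third row differs, and it is the row on which 6.1.1.1 has an explicit sentence. Treating C as missing would leave that sentence with no case to govern. Treating C as a recorded rating leaves every sentence in both sections with a use: 6.1.1.1 for ratings given, 6.4.1 for ratings never delivered.

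**2. The imputation wording.** The item on unassessable photographs concerns a missing endpoint assessment for a subject. That fits the preceding rule that two or more 'Cannot Evaluate' ratings make the overall score missing. It does not say that one evaluator's 'Cannot Evaluate' is a missing rating. The imputation model likewise works on the lift score over all evaluators, and 6.1.1.2 takes observed cases from 6.1.1.1, not 6.4.1.

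**3. Day 180.** Under 6.1.2, L, N, C has fewer than two lift ratings, so lift is not declared, and fewer than two 'Cannot Evaluate' ratings, so the score is not missing. What remains is no lift, as at Day 90.

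**4. The plan's own figure.** Inputs from SAP 3 and 6.1.1.1: assumed rate 72%, estimate at least 65%, one-sided 95% Wilson lower bound above 50%, 40 evaluable. With z = 1.645 and a = z²/n, the bound is A − √(A² − p²/(1+a)), where A = (2p+a)/(2(1+a)).

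- n = 40, 26 lifts: p = 0.650, a = 0.0676, A = 0.6405. Bound = 0.6405 − √(0.4102 − 0.3957) = 0.520. Passes.
- n = 40, 25 lifts: p = 0.625, bound 0.495. Fails both conditions.

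Success therefore needs 26 of 40. The exact power at 72% is P(X ≥ 26) = 87.6%, in line with the stated 85% or more. The type I error at 50% is 4.0%.

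**5. What the other reading could do.** Let x be the lifts among the n − 1 other subjects, with one split, and π the imputed lift probability for the split subject. 'No Lift' gives x/n; imputation gives about (x + π)/n. Imputation is never lower. It reaches 65% when π ≥ 0.65n − x.

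- n = 50, x = 32: 'No Lift' gives 32/50 = 64.0%, bound 52.4%, and fails on the estimate. The requirement is π ≥ 32.5 − 32 = 0.50. The SAP's 50-imputation Wilson formula, with a simplified model that omits site, age and BMI, gives about 65.3%, bound 53.6%, and passes in about 98% of runs.
- n = 40, x = 25: the requirement is π ≥ 26 − 25 = 1.0, so one split cannot realistically reverse the result.
- n = 40, two splits, 25 lifts among 38: 'No Lift' gives 62.5% and fails. Imputation gives about 65.8%, bound 52.4%, and passes in over 99% of runs.

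**6. How likely the pivotal count is.** Given exactly one split at n = 50, P(32 of 49) is 11.9% at a true rate of 65% and 7.1% at 72%. The documents give no frequency for splits. Purely as an illustration, if each subject had a 1% chance of one, then P(exactly one) = 50 × 0.01 × 0.99⁴⁹ = 30.6%, and 0.306 × 0.071 is about 2%.

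**The case for a change.** The strongest case for a change is that the boundary is nowhere written and that a definition costs a few sentences. A programmer working from 6.4.1, which is the section headed for incomplete evaluator data, could code 'Cannot Evaluate' as missing. There is also an incentive. The 'No Lift' rule costs power: at n = 40, with 72% lift among subjects without a split, power is 81.5% under 'No Lift' against 84.1% under imputation if 2.5% of subjects have such a split, 74.0% against 84.2% at 5%, and 56.2% against 82.9% at 10%. These split rates are assumptions.

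The missing definition stands, and so does the arithmetic. What does not stand is the claim that the primary rule is open. To impute an L, N, C subject at Day 90, the analyst would have to set aside an explicit sentence in the primary analysis section in favour of a section that never names the rating. The power cost follows from a conservative rule that the sponsor wrote down in advance. It is not a sign that the rule is uncertain.

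The Day 180 omission affects a secondary endpoint, for which neither Protocol 13.4.1.2.1 nor SAP 6.1.2 shows a success threshold in the visible text. As for the protocol's two-option question, Protocol 13 leaves further statistical detail to the SAP, and Protocol 11.2.1.1.2 leaves the evaluation method to a supporting document. Adding a non-assessable option is elaboration.

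**Conclusion.** No change to the plan follows. This is a gap in wording that analysts would fill sensibly. Day 90 has a specific rule, fixed in advance, for the pattern in question; 6.4.1 is compatible with it when read as covering ratings that were never delivered; and the Day 180 criteria lead to the same score. A cross-reference in 6.4.1 and a repeat of the split sentence in 6.1.2 would be good housekeeping, but they would alter no planned result.

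The primary conclusion could change only if the 6.1.1.1 sentence were disregarded, at least one such split occurred, and the count fell just short of 65%. Conditional on one split at n = 50, that count has a probability of 7.1% to 11.9% for true rates of 72% and 65%. The overall chance is smaller and cannot be stated, because the frequency of splits is not given. The exact counts at which a reversal is possible depend on the imputation model, and the figures here omit site, age and BMI. The worst-case ITT analysis scores the subject as no lift under either reading, so any difference would be visible in the report.

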13.4.1.1 Primary Effectiveness Endpoint

The proportion of subjects fulfilling the primary endpoint will be described by frequency statistics for the ITT subset.

Effectiveness is established if the point estimate is $\geq 65\%$ and the lower bound of the one-sided 95% Wilson CI is $> 50\%$.

In addition, the proportion of untreated individuals fulfilling the primary endpoint will be calculated. It is expected that the point estimate for the proportion of untreated individuals is $< 50\%$.

[figure not shown]

Sensitivity analyses will comprise:

- PP population with observed cases,
- ITT with observed cases, and

- ITT with missing value treated as no eyebrow lift.

CCI

Gain or loss of ≥ 2 BMI units from screening to Day 90 will be considered a major protocol deviation. Subjects with gain or loss of ≥ 2 BMI units from screening to Day 90 will be excluded from PP population. The following subgroups will be defined by the change in body weight from screening to Day 90:

- Subjects in ITT population with gain of ≥ 2 BMI units;
- Subjects in ITT population with loss of ≥ 2 BMI units; and
- Subjects in ITT population with change of < 2 BMI units.

Primary endpoint with observed cases will be analyzed in all subgroups, as defined above, with more than five subjects.

[figure not shown]

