## 3 Determination of Sample Size

A responder rate of 72% is assumed for the proportion of subjects with eyebrow lift from baseline to Day 90, as defined by the correct selection of the Day 90 standardized, photographic images by two of three independent, blinded evaluators in the previous Ulthera System eyebrow clearance study (K072505). Monte-Carlo simulations were conducted to obtain sample sizes of evaluable subjects required to achieve an improvement rate (i.e., eyebrow lift reported by two of three independent, blinded evaluators) of  $\geq$  65% and lower bound of 1-sided 95% confidence interval (CI) above 50%. To achieve this threshold with  $\geq$  85% power, a sample size of 40 evaluable subjects will be required. Assuming a maximum attrition of 10 subjects, approximately 50 subjects will be enrolled. In Stage 1, 10 subjects will be enrolled, while all other subjects will be enrolled in Stage 2. Because a sample size of 40 subjects who complete the full Ultherapy treatment session is required, study enrollment will continue until the required number of treated subjects is achieved.

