## 4.2 Intent-to-Treat Population (ITT)

The Intent-to-Treat population (ITT) consists of all subjects who are enrolled.

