# 5 Endpoints for Analysis

## 5.1 Effectiveness Endpoints

### 5.1.1 Primary Effectiveness Endpoint

The primary endpoint of the study is the proportion of treated subjects with eyebrow lift, as demonstrated by comparing photographs taken at Day 90 (post-treatment) with baseline (pre-treatment) photographs. If the subject's screening photograph (Visit 1) is deemed acceptable upon review by the central photography vendor, it will default to the baseline (pre-treatment) photograph and will be used for reference throughout the study.

[figure not shown]
- Lift is concluded if at least two of three independent, blinded evaluators report "eyebrow lift" in the Day 90 standardized, photographic images when compared to baseline photographic images.
- The success criterion is defined by achieving simultaneously a point estimate  $\geq 65\%$  and a lower bound of the one-sided 95% Wilson confidence interval  $> 50\%$  for the proportion of subjects with eyebrow lift.

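### With 10 of 50 outcomes missing, 50 imputations leave the pooled lift rate with a Monte Carlo SD of about 0.45 to 0.5 points, and the hard 65% cut makes no allowance for it

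*SAP*

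**What the plan says.** SAP 5.1.1 sets a two-part rule for the primary endpoint: "The success criterion is defined by achieving simultaneously a point estimate" of at least 65% and a one-sided 95% Wilson lower bound above 50%. Protocol 13.4.1.1 has the same rule.

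The primary analysis is on the ITT population: "The Intent-to-Treat population (ITT) consists of all subjects who are enrolled". Subjects without a usable Day 90 outcome therefore stay in the denominator and are imputed. SAP 6.1.1.1 says "Imputation is done 50 times using a fully conditional specification logistic regression method", and that the model "will use the investigational site and the baseline characteristics age and BMI as independent variables". Condition A compares the mean of the 50 imputed proportions with 65%. Condition B compares a multiple-imputation Wilson bound with 50%. With complete data nothing is imputed.

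The planning figures are in SAP section 3: "Assuming a maximum attrition of 10 subjects, approximately 50 subjects will be enrolled".

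No random seed appears in the visible text. The SAS code is blacked out, so whether one is fixed cannot be judged.

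**The concern.** The mean of 50 imputed proportions is a random quantity, because rerunning the same model on the same data with another seed gives a slightly different value. Condition B allows for the finite number of imputations through the between-imputation variance and the t quantile. Condition A has no such allowance: 65.0% passes and 64.9% fails.

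Fifty imputations are usually ample for a standard error. They are less comfortable when the pooled point estimate itself is held against a fixed cut. At stake is the primary verdict in a trial that lands close to 65%, where success could turn on a seed rather than on the data.

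**Working it through.** **1. The plan's own figure.** The inputs from SAP section 3 are an assumed lift rate of 72% and "85% power, a sample size of 40 evaluable subjects will be required". At n = 40 the smallest count meeting both conditions is 26 (26/40 = 65.0%, Wilson lower bound 52.0%). The exact power, P(X ≥ 26) for a binomial with n = 40 and p = 0.72, is 87.6%. At n = 38 it is 84.9% and at n = 39 it is 82.2%. The planned 40 is reproduced. The passing count at that size sits exactly on the 65% cut, and exactly 26 of 40 has probability 8.3% at a true rate of 72%.

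**2. Monte Carlo SD of the pooled rate.** Let N = 50 be the number enrolled, k the number missing, p = 0.65 the rate at the cut and m the number of imputations. For an intercept-only model the between-imputation variance is

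B = k·p(1−p)/N² + (k/N)²·p(1−p)/(N−k), and SD = √(B/m).

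With k = 10: B = 10 × 0.2275/2500 + 0.04 × 0.2275/40 = 0.00091 + 0.00023 = 0.00114. With m = 50, SD = √(0.00114/50) = 0.0048, or 0.48 points. The difference between two seeds has SD 0.48 × √2 = 0.68 points.

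| Missing of 50 | SD at m = 50 (points) |
|---|---|
| 0 | 0 |
| 1 | 0.14 |
| 2 | 0.19 |
| 3 | 0.24 |
| 5 | 0.32 |
| 8 | 0.42 |
| 10 | 0.48 |

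Simulation with five equal sites, age and BMI in the model gives about 0.45 points with 10 missing and 0.30 with 5.

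**3. Which condition decides.** At a pooled 65.0% with 10 missing, r = 1.02 × 0.00114/(0.2275/50) = 0.255, and the SAP's formula gives a lower bound of 51.9%. With 2 missing it is 53.1%. Condition B is already met at the cut, so the verdict there rests on condition A.

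**4. How often two seeds disagree.** Each simulated data set was imputed twice at m = 50 with independent random streams, using the model with site, age and BMI.

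| Situation | Opposite verdicts |
|---|---|
| 10 missing, 26/40 observed lifts | about 17% |
| 10 missing, 27/40 observed lifts | about 3 to 5% |
| 10 missing, all trials, true rate 68 to 72% | about 2% |
| 5 missing, all trials | about 0.8 to 1.2% |
| 2 missing, all trials | about 0.3 to 0.9% |

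The ranges reflect simulation error and differences between runs. In the intercept-only model 26/40 passes on about 46% of seeds. With covariates, the expected pooled rate for 26/40 moves away from 65% in most data sets, and only about 38% of them are truly seed-dependent (between 5% and 95% of seeds pass).

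**5. Effect of a larger m, with 10 missing.** The formula gives SDs of 0.15 points at m = 500, 0.11 at 1,000 and 0.05 at 5,000; simulation with covariates gives about 0.10 at 1,000. At m = 1,000 two seeds disagree in about 0.3 to 0.6% of all trials and in about 4% of cases at 26/40.

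**The case against.** The case for leaving the plan alone has four parts.

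- **Ten missing is the stated maximum.** With few losses the noise is small, and with none it vanishes. This stands, and the size must always be quoted with the number missing. A reader might take half a point as a fixed property of 50 imputations. The documents do not support that, because it applies only if all 10 allowed losses lack a Day 90 outcome.
- **The noise is small beside sampling error.** At a 72% rate and n = 50 the sampling SD is √(0.72 × 0.28/50), about 6.3 points, so 0.48 points adds (0.48/6.3)², or about 0.6%, to the variance. This also stands. No bias, type I error inflation or material loss of power has been shown.
- **A seed may be fixed in the blacked-out code.** It may. A reader might infer that two statisticians following the SAP would reach opposite conclusions. That holds only if no seed is fixed, which the documents do not show. A fixed seed gives repeatability, but near 65% another equally valid seed could still reverse the verdict.
- **Analyses without random draws are pre-specified.** SAP 6.1.1.2 has observed-case analyses on PP and ITT and a missing-as-no-lift analysis. They would show that a close result is fragile, but they do not decide success.

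**Conclusion.** The point holds in a limited form. At the planned maximum loss, the quantity compared with 65% carries a Monte Carlo SD of about 0.45 to 0.5 points that the success rule ignores. The verdict can then depend on the seed when the pooled rate lies within about 1 point of the cut. That is a narrow band, and the effect shrinks as fewer outcomes are missing.

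These sizes assume 50 enrolled, five equal sites, and covariates unrelated to lift. The observed amount of missing data is not known from the documents. Because the randomness is avoidable at almost no cost, it is worth removing, but as a low-priority improvement and not as a flaw that threatens the trial.

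**What to change.** Before the reader ratings are transferred:

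- In SAP 6.1.1.1, raise the number of imputations from 50 to at least 1,000, and preferably about 5,000. Make the same change in SAP 6.1.2 for the Day 180 photographic endpoint, so that both use one method.
- Confirm that the seed is already specified in the blacked-out code, or state it in the SAP.
- Report the Monte Carlo standard error of the pooled rate, √(B/m), beside the comparison with 65%.

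A larger m reduces the dependence on the seed but does not abolish it, which is why the standard error should be shown. The timing matters, because changing m or the seed after a close result would look like choosing the answer. The cost is a few edited lines and a few minutes of computing. Endpoint, thresholds and sample size stay as they are.
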